### **13.8 Evaluation of Response**

All participants in the study who complete the PHQ-9 and GAD-7 at Week 13 will be evaluable for response to the intervention. In sensitivity analyses, we will evaluate how imputation of these values utilizing either baseline or Week 7 data impact study conclusions. Note that this is a feasibility study and analyses of the intervention effects will be used to plan future studies, not to demonstrate efficacy.

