### 13.5 Secondary Objectives, Endpoints, Analysis Plans

For Objective 1.2.1, baseline descriptive statistics will be compared by intervention arm using chi-square tests for categorical variables and ANOVA for continuous variables. Due to randomization, we do not anticipate differences by intervention arm; if they are found, we will adjust for them in the analyses for Objectives 1.2.1, 1.2.2, 1.2.3, and 1.2.4. The Working Alliance Inventory will be summarized using descriptive statistics.

Depression and anxiety outcomes (PHQ-9 and GAD-7) will be analyzed using mixed-model analysis of covariance (ANCOVA) to account for intra-individual correlations among longitudinal measures. The model will contain terms for the intervention group, baseline value of the outcome, therapist or site staff person completing check-in calls, psychotropic medications use, a time effect (mid-, post-intervention), and the time by intervention interaction term (to test whether the intervention effects vary by time). Because participants may exhibit moderate or severe levels of either depression or anxiety, we will create a combined variable that indicates if a participant had moderate/severe depression or anxiety at mid- or post-intervention. Each stepped-care telehealth group will be compared with EUC using a GEE approach with a logit link to determine if rates of the combined outcome differ at mid- or post-intervention. Other outcome measures (sleep disturbance, fatigue, fear of recurrence, cancer-related distress, and quality of life) will be analyzed using ANCOVA at week 13 to meet objective 1.2.2.

For Objective 1.2.3, we will calculate total cost of the stepped-care telehealth (low intensity, high intensity) and the EUC interventions and average cost/survivor screened and randomized to each trial arm. Total cost includes costs of intervention implementation and health care costs for each participant.

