### **13.7 Reporting and Exclusions**

Unless we receive written or verbal withdrawal of consent, we will try to reach every participant for telephone calls, telephone sessions, and assessments as outlined in the protocol.

The dataset used in the analysis of Objective 1.1.1 will include all eligible participants to calculate recruitment rates. Accrual, retention, and adherence will be calculated on the participants who consent to participate in the study. The analysis of the secondary objectives and exploratory objective will include all participants who consent to participate in the study. The ANOVA models used for the secondary objectives use data from all available time points and allows for data to be missing at random. For the analyses of the secondary objectives and the exploratory objective, we will use an intent-to-treat approach. If participants are moved from low intensity to high intensity they will be analyzed using the

low intensity assignment (intent to treat). In exploratory models, we will analyze the impact of adherence by including it as a predictor.

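### Section 13.8 defines a Week 13 completer set that conflicts with the Section 13.7 population and the Section 13.5 mixed model, and the handling of missing Week 13 data is weak

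*Combined protocol and SAP*

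**What the plan says.** Section 13.7 sets the population: "The analysis of the secondary objectives and exploratory objective will include all participants who consent to participate in the study". It adds that "The ANOVA models used for the secondary objectives use data from all available time points and allows for data to be missing at random", and then "For the analyses of the secondary objectives and the exploratory objective, we will use an intent-to-treat approach".

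Section 13.5 gives PHQ-9 and GAD-7 (Objective 1.2.1) a mixed-model ANCOVA with baseline value, time (mid- and post-intervention) and time-by-intervention terms. The sleep, fatigue, fear-of-recurrence, cancer-distress and quality-of-life outcomes "will be analyzed using ANCOVA at week 13 to meet objective 1.2.2"; the covariates of that model are not listed. Section 13.6 also uses ANCOVA at Week 13 for the Objective 1.3.1 subgroups, and these include PHQ-9 and GAD-7.

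Section 13.8 then says "All participants in the study who complete the PHQ-9 and GAD-7 at Week 13 will be evaluable for response to the intervention", followed by "In sensitivity analyses, we will evaluate how imputation of these values utilizing either baseline or Week 7 data impact study conclusions".

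The schedule matters here. Under Section 7.6 the only outcome scales collected at Week 7 are PHQ-9 and GAD-7. The Objective 1.2.2 instruments are collected at baseline (Section 7.4) and Week 13 (Section 7.7) only.

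**The concern.** Sections 13.7 and 13.8 describe different sets for the same two scales. Response is not defined as an endpoint anywhere, so an analyst cannot tell whether Section 13.8 governs a separate analysis, restricts the Section 13.5 model, or governs nothing.

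The Week 13 ANCOVAs have a related problem. They cannot include all consenting participants once Week 13 values are missing. They also leave unused the Week 7 PHQ-9 and GAD-7 of people who later drop out, which are the best available evidence on why those people left. Contact differs sharply between weekly therapy, biweekly calls and enhanced usual care (Section 7.1), so drop-out that depends on symptoms differently by arm is plausible.

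Section 13.3 says that effect sizes will inform the larger trial. The cost of an unclear population or a poor missing-data method is therefore a distorted planning value.

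**Working it through.** **1. Who is in which set.** Taking the text as written:

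| Post-baseline PHQ-9/GAD-7 data | 13.7 population | 13.5 mixed model | 13.8 evaluable | Week 13 ANCOVA |
|---|---|---|---|---|
| Week 7 and Week 13 | yes | yes | yes | yes |
| Week 13 only | yes | yes | yes | yes |
| Week 7 only | yes | yes | no | no |
| Neither | yes | contributes nothing | no | no |

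(The last column assumes that the Week 13 questionnaires are missing when the Week 13 interview is.) The third row is the conflict. The fourth shows that even the mixed model cannot use literally everyone.

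**2. Size of the affected group and the plan's own precision.** Inputs from Section 13.3: 45 per group, 20% drop-out, SDs of change 5.8 (PHQ-9) and 4.2 (GAD-7). The confidence level is not stated for this figure; two-sided 95% reproduces it.
- Completers: 45 × (1 − 0.20) = 36 per group, so 90 − 72 = 18 without Week 13 data.
- Half-width: 1.96 × √(2/36) = 0.462 SD (stated 0.46). Times 5.8 = 2.68 (stated 2.7); times 4.2 = 1.94 (stated 1.9).
- If all 45 per group gave full information: 1.96 × √(2/45) = 0.413 SD, or 2.4 and 1.7 points.

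The planned precision thus rests on Week 13 completers. The mixed model falls between ±0.46 and ±0.41 SD. Where it falls depends on the Week 7 to Week 13 correlation and on who has Week 7 data, and the documents give neither.

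**3. When the Week 13 ANCOVA is valid.** In one arm let p be the drop-out proportion, and D the points by which drop-outs' Week 13 scores would be worse than those of completers with the same covariates. If C is the completer mean, the full-arm mean is C + pD, so the completer mean looks better by pD. The error in the effect is −(p₁D₁ − p₀D₀), with 1 for intervention and 0 for usual care. With p = 0.20 in both arms, a true effect of −2 and assumed values of D:
- D₁ = D₀ = 2: error 0, estimate −2.0.
- D₁ = 2, D₀ = 0: error −0.4, estimate −2.4 (D₁ of 1 to 3 gives −2.2 to −2.6).
- D₁ = 2, D₀ = −2: error −0.8, estimate −2.8.

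The analysis is unbiased when D is zero or when pD is equal in the two arms. The part of D that Week 7 scores predict can be recovered by an analysis that uses those scores, and not by one that omits them.

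**4. The sensitivity analysis.** Assume mean changes of −3 (usual care) and −5 (intervention), a true effect of −2, and drop-outs who would have changed as completers did in their arm. Carrying baseline forward sets their change to zero, so the estimate is (1 − p₁)(−5) − (1 − p₀)(−3):
- 20% in each arm: −4.0 + 2.4 = −1.6.
- 10% usual care, 30% intervention: −3.5 + 2.7 = −0.8.
- 30% usual care, 10% intervention: −4.5 + 2.1 = −2.4.

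The assumed changes are not in the documents. Carrying Week 7 forward is not evaluated, because it needs an assumed Week 7 change.

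**The case against.** The strongest reply is that Sections 13.5 and 13.7 already agree on PHQ-9 and GAD-7: a mixed model, all available data, missing at random, analysis by initial assignment. Section 13.8 names no model and does not say that anyone is removed from that one. This stands. A reader might infer that the main analysis is completers-only, but the text does not say so. What it leaves is an unresolved conflict over population.

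A reader might also infer that the Week 13 ANCOVA for Objective 1.2.2 contradicts the statements in Section 13.7 on time points and missing data. It does not. Those instruments have no Week 7 measurement, so baseline and Week 13 are all their time points, and complete-case ANCOVA is valid under missing at random given its covariates. Nor does it breach intent-to-treat in the sense Section 13.7 illustrates, which is analysis by assigned intensity. The condition in step 3 remains, as does the plain fact that this ANCOVA cannot include everyone.

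Third, Section 13.8 speaks of "imputation of these values utilizing either baseline or Week 7 data" and does not name carry-forward; a regression or multiple imputation would fit the words. That is fair, and the method is best called unspecified. Carry-forward is still the most natural reading of using either one value or the other.

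Finally, Section 7.2 provides reminders, re-mailing and telephone completion, and Section 13.8 says that effect analyses are for planning and not for demonstrating efficacy. Both points lower the severity. Neither settles which set governs.

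**Conclusion.** The point holds as a conflict of populations and a gap in missing-data handling. Section 13.8 and the model in Sections 13.5 and 13.7 treat participants with Week 7 but no Week 13 scores differently. At planned drop-out that is at most 18 of 90, and fewer if some of them also missed Week 7. The precision at stake is bounded: ±0.46 SD on completers against ±0.41 SD at best.

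For Objectives 1.2.2 and 1.3.1, any bias depends on drop-out being related to Week 7 symptoms, beyond the covariates, differently by arm. The documents cannot say whether that will happen. The subgroup ANCOVA is the weaker of the two, because for PHQ-9 and GAD-7 it discards Week 7 values of the outcome itself.

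The range −0.8 to −2.4 should not be read as bias from the completer set. Under the assumptions of step 4 a completers-only analysis would recover −2. The range shows only what carrying baseline forward can do when both arms fall from elevated entry scores. Severity is modest.

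**What to change.** - **Section 13.8:** state that the Objective 1.2.1 estimates come from the Section 13.5 mixed model on all randomised participants with any Week 7 or Week 13 PHQ-9 or GAD-7 value. Delete the evaluable sentence, or relabel it as a descriptive count of Week 13 completers.
- **Section 13.7:** limit the sentence on all available time points to that mixed model.
- **Sections 13.5 and 13.6:** for Objectives 1.2.2 and 1.3.1, list the ANCOVA covariates and use multiple imputation by arm, with baseline values and Week 7 PHQ-9 and GAD-7 as auxiliary variables. The PHQ-9 and GAD-7 subgroups may use the mixed model instead.
- **Sensitivity analysis:** replace single-value imputation from baseline or Week 7 with multiple imputation, and use a delta-adjusted version to show how far departures from missing at random move the estimates.

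The cost is a change of SAP wording and a little extra analysis work. All the data needed are already scheduled for collection.
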